8.4 Blinding

No blinding procedure will be performed. The patient will be blinded, with respect to the respiratory-treatment, due his medical status.

8.4.1 Emergency procedure for unblinding

Not applicable.

8.4.2 Unblinding-procedure at the end of the clinical investigation.

Not applicable.

8.5 Benefit and risk assessment

Both the Infinity Delta Monitor and the Evita Infinity V500 are part of the clinical routine ICU therapy. Also, the ventilator mode conventional PSV and variable PSV are part of the clinical routine ICU therapy. The only procedures performed in the present cross-over trial is that the ventilator mode will be changed from conventional PSV to variable PSV or vice versa. Therefore, there are no actual risks for the patients during the present study or clinical ICU routine therapy. The only additional procedures attributed to this study is that extra arterial blood gas measurements will be performed during the study. These risks are low, as the person performing the study will be trained in taking arterial blood gas analysis and such procedures are taken also routinely during ICU stay.

8.6 Clinical investigation procedures

8.6.1 General rules for clinical investigation procedures

- All investigation measures have to be documented with date (dd.mm.yyyy).

- The dates of all procedures should be according to the clinical investigation plan (CIP). The time margins mentioned in the clinical investigation flow chart are admissible. If, for any reason, a clinical investigation procedure is not performed within scheduled margins a CIP deviation should be noted, and the procedure should be performed as soon as possible or as adequate.

8.6.2 Screening investigation

All patients scheduled for ICU will be screened. Eligible patients will be included in the study. Informed patient consent will be taken after the patients have been extubated and transferred to the normal ward.

8.6.3 Treatment

The treatment includes setting the ventilator to conventional PSV mode for one hour and variable PSV mode for one hour (in total 2 hours of treatment per patient, randomized fashion). Arterial blood gases taken at the beginning and the end of each ventilator mode (2x per mode, in total 4 arterial blood gases per patients) will be taken in addition to the clinical routine therapy. Thereafter, the treatment will be terminated and no patient follow up will be performed.

8.6.4 Laboratory Tests

Blood gas analysis will be taken at the beginning and the end of each treatment (2 times 2 arterial blood gas analyses, in total 4 blood gas analyses per patient).

8.6.5 End-of-clinical investigation (EOI) examination

No end-of-clinical-investigation (EOI) examination will be performed.

9. SAFETY DEFINITIONS AND REPORTING REQUIREMENTS

9.1 Adverse events (AEs)/Adverse device effects (ADEs)

9.1.1 Summary of known and potential risks of the medical device

Both the Infinity Delta Monitor and the Evita Infinity V500 are part of the clinical routine ICU therapy. These devices are licensed for the clinical usage and will be used only for their specific purpose. Therefore, there are no extra risks associated with this clinical study. Theoretical risks include failure of the device with harm to the patients. In case of technological failure of the devices the subject may be harmed as monitoring of vital parameters (Infinity Delta Monitor) or mechanical ventilation (Evita Infinity V500) might be inadequate, injurious or in theory lethal.

9.1.2 Definition of adverse event and adverse device effect

Adverse events (AEs) are any significant hemodynamic or respiratory impairment (e.g. in- or decrease of systolic or diastolic arterial blood pressure or heart rate or parameters of respiration of < or >30% baseline). Further, any technological problems are defined adverse device effects (ADEs). Such impairments are not expected during the present study.

9.2 Serious adverse events (SAEs)/Serious adverse device effects (SADEs)

Serious adverse events (SAEs) are hemodynamic or respiratory impairments (see AEs) that are potentially life-threatening to the subject. Serious adverse device effects (ADEs) are technological problems that are potentially life-threatening to the subject.

9.2.1 Hospitalization – Prolongation of existing hospitalization

Not applicable.

Heartrate variability during mechanical pressure support ventilation – comparing conventional and variable pressure support ventilation: a cross-over trial

9.2.2 SAEs /sADE related to study-mandated procedures

Not applicable.

9.2.3 Pregnancy

Women, who are known to be pregnant before taking part in the study, are excluded.

9.3 Severity of adverse events/adverse device effects

Not applicable.

9.4 Relationship to medical device

There is no financial or other relationship between the authors/investigators and the manufacturer of the medical devices used.

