9.5.1 Reporting procedures for SAEs/SADEs

SAEs and SADEs will be reported within 24 hours to the ethical care committee and the study will be paused until clarity about the SAEs/SADEs reason.

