11.6.3 Safety and tolerability endpoints

The occurrence of adverse events will be described descriptively by frequencies and percentages.

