11.6.4 Exploratory analyses

All exploratory parameters, which are obtained from arterial blood gas analysis (systolic and diastolic arterial blood pressure, arterial partial pressure of oxygen, arterial partial pressure of carbon dioxide) will be described with descriptive statistics (boxplots, means, standard deviations, medians and quartiles) separately for the two groups.

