11.7 Interim analysis

No interim analysis is planned.

Criteria for the termination of the clinical investigation:

Not applicable as no interim analysis planned.

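### Section 9.4 holds a financial-ties statement where the relationship of adverse events belongs, so harm from the ventilation mode is neither attributed nor graded under the stated rules

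*Protocol*

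**What the plan says.** Chapter 9 of the protocol sets the safety definitions and reporting rules.

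- Section 9.4, between severity (9.3) and reporting (9.5), consists of one sentence: "There is no financial or other relationship between the authors/investigators and the manufacturer of the medical devices used".
- Section 9.3 on severity reads "Not applicable". Section 9.2.2, on serious events related to study-mandated procedures, carries the same entry.
- Section 9.1.2 defines adverse events as significant haemodynamic or respiratory impairment, with a change beyond 30% of baseline as the example. It defines adverse device effects as technological problems. Section 9.2 makes either serious if potentially life-threatening.
- Section 9.5.1 requires serious events to be reported within 24 hours, and "the study will be paused until clarity about the SAEs/SADEs reason".
- Section 11.6.3 gives the whole safety analysis: "The occurrence of adverse events will be described descriptively by frequencies and percentages".
- Section 11.6.4, in contrast, describes the exploratory parameters "separately for the two groups", and 11.6.1 does the same for the primary endpoint.
- Section 11.1 names one analysis set, per-protocol, limited to patients treated with both modes. Drop-outs are excluded.
- Sections 8.2.11 and 8.5 state that the arterial blood gas samples are additional to routine care. Section 8.2.11 names infection and bleeding as potential risks if they are done inappropriately.

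**The concern.** The heading and position of 9.4 call for a judgement about the event: was it related to the device or treatment under study? The text is instead about the investigators' ties to the manufacturer, so the judgement is not set up anywhere. This is wrong content in a section, and more than detail left for later. A statistical analysis plan can tabulate relatedness only if the protocol has someone assess it.

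Two things are at stake. First, the comparison is between two ventilation modes on the same ventilator. The harm of most interest is a physiological reaction to the mode while the device works as intended, and the definitions give that event no attribution and no grade. Second, the protocol relies on attribution in its own pause rule. Resumption after a serious event depends on its reason being clear, but no assessor, criteria or record is named.

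**Working it through.** The point rests on text, so the sections are set side by side first. Figures follow where they help.

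**1. What the definitions do with each kind of event (9.1.2, 9.2, 9.2.2, 9.3, 9.4)**

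| Event | Class | Relationship recorded | Severity grade |
|---|---|---|---|
| Ventilator or monitor fault | Adverse device effect | Device fault, by definition | None |
| Circulatory or respiratory impairment under variable PSV, device working | Adverse event | None | None |
| The same under conventional PSV | Adverse event | None | None |
| Bleeding or infection from a study blood sample | Adverse event only if it impairs circulation or respiration | None; 9.2.2 set as not applicable | None |

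Rows two and three receive the same entry, although the difference between them is what a tolerability comparison needs. Row four is set aside in 9.2.2, while 8.2.11 and 8.5 describe the sampling as study-specific and as carrying a risk. Seriousness is defined in 9.2, so what is missing is a grade for the events below that level.

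**2. The pause rule.** Section 9.5.1 requires clarity about the reason. Section 9.4 is where the means of reaching it would stand, and it contains none. No other section names an assessor or categories.

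**3. Presentation by mode.** Sections 11.6.1 and 11.6.4 ask for it; 11.6.3 does not. Section 8 runs the two hours back to back, and 8.6.1 asks only for the date of investigation measures. A date alone does not place an event in a mode.

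**4. Analysis set.** The plan's sample size is reproduced first. Section 11.2 gives a difference of 10 ms² and a standard deviation of the difference of 25 ms², so d = 10/25 = 0.4. With a two-sided 0.05 one-sample t-test, the exact noncentral-t power is 0.7999 at n = 51 and 0.8078 at n = 52. The stated 52 is correct. The allowance is 60 − 52 = 8 patients, and 8/60 = 13.3%. The reasons listed in 11.2 include unstable cardiovascular or pulmonary conditions and cardiac arrest. Some of these 8 would therefore be patients with an adverse event, and the per-protocol set excludes them. The list also includes technological failure and emergencies, so 8 is the allowance for all causes and not a count of adverse events.

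**5. Assumed illustration of why mode matters.** The count is invented; the protocol gives no event rate. Suppose 6 of 60 patients have one event each. Without a split, the summary is 6/60 = 10%. If all 6 arose under variable PSV, the exact two-sided sign test gives 2 × 0.5⁶ = 0.031. If 3 arose under each mode, p = 1.0. An unsplit percentage is the same in both cases.

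**6. Limit on what any coding could show.** With no events in n patients, the one-sided 95% upper bound is 1 − 0.05^(1/n): 4.9% for n = 60 and 5.6% for n = 52.

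**The case against.** The other side has several fair arguments.

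- **The split by mode is a table matter.** Section 11.6.3 does not say that the modes are pooled and names no denominator, and a statistical analysis plan could add the split. This stands. A reader might infer that the planned output is one pooled percentage of 60, but the text does not say so. Withdrawn patients are also replaced (7.3.2), so more than 60 may be exposed. The missing split is a supporting point only.
- **Mode at onset may be recoverable.** Section 5.2 records all respirator data, and the order is known from randomization. Section 7.3.1 has withdrawal reasons recorded in detail, and 11.1 has interruptions documented. The form itself is not shown, and the date rule in 8.6.1 is a general minimum. This also stands: the protocol does not require onset time and mode for an event, but they may well be available.
- **The pause can still be lifted.** A reader might infer that the trial is unable to meet its own condition. Section 9.5.1 itself demands that the reason be clarified, so an inquiry is mandated for serious events. What is missing is who conducts it, how, and where it is recorded.
- **Termination criteria.** A reader might see a contradiction between the pause rule and 11.7, which says "Not applicable as no interim analysis planned". That entry sits under interim analysis and concerns statistical stopping. Sections 7.4 and 13.2.1 already allow closure with notification. There is no contradiction.
- **Comparative safety is not an objective.** Two hours of routine modes in about 60 patients give limited evidence on harm, as the bounds of 4.9% to 5.6% show. This limits the consequence. It does not explain a section with the wrong content, and tolerability is a listed endpoint in the synopsis.

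**Conclusion.** The point holds as a defect in the document. Section 9.4 carries unrelated text, 9.3 and 9.2.2 are marked not applicable, and device effects are confined to technological problems. As a result, an event caused by the ventilation mode on a working device is never attributed or graded under the stated rules, and the pause rule in 9.5.1 rests on a judgement with no assessor or method. Two weaker points add to this: 11.6.3 does not ask for events by mode, and the per-protocol set, read literally, removes patients whose event ended treatment. Up to 8 of 60 (13.3%) may be lost for all causes on the plan's own allowance.

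The conclusion assumes that no other document at the site defines relatedness and severity, and that 11.1 applies to safety because no other set is named. It does not mean that harm could never be traced to a mode, nor that a paused study could never resume. The efficacy analysis and the sample size of 52 are unaffected. It should be corrected, because the pause rule and the tolerability endpoint both use this information.

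**What to change.** - **9.4:** replace the text with the investigator's judgement of each event's relationship to (a) the ventilation mode in force at onset, (b) the device and (c) the study blood sampling, with stated categories. Move the financial statement elsewhere.
- **9.3 and 9.2.2:** replace the not-applicable entries with a simple severity grade in 9.3 and a reference to 9.4 in 9.2.2.
- **Case report form:** record the onset time of each event and the mode in force, if the form does not already do so.
- **11.6.3:** report frequencies and percentages by mode at onset, among all patients who started that mode, and state that the per-protocol set does not apply here. Patients who stop in the first hour then count only for the mode they received.
- **9.5.1:** refer to the 9.4 assessment and name the role that documents it.

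The cost is protocol wording, a few form fields and one table split by mode. It needs no extra patients, visits or procedures.

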9.5 Reporting procedures

AEs or ADEs will be reported within one week to the ethical care committee.

9.5.1 Reporting procedures for SAEs/SADEs

SAEs and SADEs will be reported within 24 hours to the ethical care committee and the study will be paused until clarity about the SAEs/SADEs reason.

10. FOLLOW-UP

10.1 Follow-up of clinical investigation participants including follow-up of adverse events

No follow-up of clinical investigation participants will be performed.

10.2 Treatment after end of clinical investigation

The clinical investigation has no effect on the treatment of the patient especially not after its end.

11. STATISTICAL METHODOLOGY AND ANALYSIS

11.1 Analysis sets

The study will be analyzed using the per-protocol set. This analysis set comprises all subjects who underwent treatment with both pressure support systems and did not violate the protocol in a way that might affect the evaluation of the primary study parameter. Drop-outs may occur if the treatment will be interrupted in case of technological failure, emergency situation, unstable cardiovascular or pulmonary conditions, cardiac arrest and cardiopulmonary reanimation. In case of a drop-out, the evaluation of the primary parameter is not meaningful so that drop-outs will be excluded from the analysis. All treatment interruptions will be documented and summarized.

Violations of the protocol due to a wrong randomization ordering (reverse than randomized) are less likely because measurements are done by one person ([name]) who is also the holder of the randomization list.

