EXCLUSION CRITERIA	
patients aged < 18 or > 80 years
 
patients with active heart pace maker / defibrillator
 
patients with absent sinus rhythm in electrocardiogram
 
patients with known severe disease of autonomous nervous system
 
women, who are already known to be pregnant before taking part in this study

COMPARATIVE DEVICE	None.
CONCOMITANT MEDICATION/CON-COMITANT DEVICE	Every therapy / medication / monitoring is allowed as indicated per routine.
EFFICACY ENDPOINTS	
Primary study endpoint:
 
High frequency components (HF) of Heart Rate Variability (median over one hour measurement per patient)
 
Secondary study endpoints:
 
Applied tidal volumes and other heart rate variability parameters (standard deviation of R to R intervals (SDNN), high frequency to low frequency ratio),
 
Exploratory endpoints:
 
physiological parameters (systolic and diastolic arterial blood pressure, arterial partial pressure of oxygen, arterial partial pressure of carbon dioxide).

TOLERABILITY / SAFETY ENDPOINTS	The occurrence of adverse events will be documented.
QUALITY OF LIFE	No quality of life parameters will be measured.
STATISTICAL METHODOLOGY	
Primary Endpoint
 
High frequency components (HF) of Heart Rate Variability (median over one hour measurement per patient)

Secondary Endpoints 
Applied tidal volumes and other heart rate variability parameters (median of standard deviation of R to R intervals (SDNN) or high frequency to low frequency ratio over one hour measurement per patient)

Exploratory Endpoints 
Physiological parameters (systolic and diastolic arterial blood pressure, arterial partial pressure of oxygen, arterial partial pressure of carbon dioxide).

Null and alternative hypotheses: 
Null hypothesis of primary endpoint: there is no difference in the mean heartrate variability (measured as median high frequency components HF over one hour measurement per patient) between variable/noisy pressure support mechanical ventilation compared to conventional pressure support mechanical ventilation.

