7.3 Withdrawal and replacement of subjects

7.3.1 Criteria for withdrawal

Discontinuation from the study is to be understood when the subject did not undergo the end of study (EOS) examination and/or all pivotal assessments during the clinical investigation.

Subjects must be withdrawn under the following circumstances:

- at their own request
- if the investigator feels it would not be in the best interest of the subject to continue
- if the subject violates conditions laid out in the consent form / information sheet or disregards instructions by the clinical investigation personal

- in case of severe medical emergency (e.g. cardiac arrest, reanimation)

In all cases, the reason why subjects are withdrawn must be recorded in detail in the case record file (CRF) and in the subject's medical records. Should the clinical investigation be discontinued prematurely, all clinical investigation materials (complete, partially completed and empty CRFs) will be retained.

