7.3.2 Follow-up of patients withdrawn from the clinical investigation

In case of premature discontinuation, no follow-up will be performed. Replacement policy

Patients excluded from the study for any of the reasons above will be replaced.

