11.3 Relevant protocol deviations

Protocol deviations may occur if the treatment will be interrupted in case of technological failure, emergency situation, unstable cardiovascular or pulmonary conditions, cardiac arrest and cardiopulmonary reanimation. In case of a drop-out, the evaluation of the primary parameter is not meaningful, so that drop-outs will be excluded from the statistical analysis.

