11.5 Missing, unused and spurious data

Missing, unused or spurious data due technological failure, emergency situation, unstable cardiovascular or pulmonary conditions, cardiac arrest and cardiopulmonary reanimation will be reported and presented. Records with missing data will be excluded from the analysis.

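### Read as written, the per-protocol set and the drop-out exclusion also apply to the adverse-event percentages, which then leave out patients who drop out because of instability, arrest or reanimation

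*Protocol*

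**What the plan says.** Section 11.1 of the protocol: "The study will be analyzed using the per-protocol set". Membership requires treatment with both ventilation modes and no violation that might affect the primary parameter. The section lists the causes of drop-out (technical failure, emergency, unstable circulation or respiration, arrest, reanimation). It then excludes drop-outs from the analysis because the primary parameter cannot be meaningfully evaluated in them.

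Section 11.3 repeats the list and the reason, and concludes that "drop-outs will be excluded from the statistical analysis". Section 11.5 adds: "Records with missing data will be excluded from the analysis".

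The synopsis gives one tolerability and safety endpoint: "The occurrence of adverse events will be documented". Its analysis, in section 11.6.3, is a single sentence: "The occurrence of adverse events will be described descriptively by frequencies and percentages". It states neither a set nor a denominator. The protocol names no safety or all-treated set anywhere.

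Section 7.3.1 lists a severe medical emergency, with arrest and reanimation as examples, among the reasons for compulsory withdrawal. Section 7.3.2 then says "Patients excluded from the study for any of the reasons above will be replaced".

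**The concern.** The exclusion is tied to the outcome being counted. Section 9.1.2 defines an AE as a significant haemodynamic or respiratory impairment, and section 9.2 makes it serious if it is potentially life-threatening. Cardiovascular or pulmonary instability, arrest and reanimation fit these definitions, and an emergency may. Section 11.2 itself describes the expected drop-out as intervention-related.

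The stated reason for the exclusion is sound for HF: without two usable recordings there is no paired difference. It does not carry over to AEs, since a patient who becomes unstable has a perfectly usable AE record. If section 11 is applied as it stands, the only safety endpoint is summarised in a group selected partly for not having had the events of interest.

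**Working it through.** **Step 1: the protocol's own numbers.** Section 11.2 assumes a mean difference of 10 ms² and a standard deviation of the difference of 25 ms², so the standardised effect is 10/25 = 0.4. For a two-sided one-sample t-test at 0.05, the noncentral t distribution gives power 0.7999 at n = 51 and 0.808 at n = 52. The stated 52 for 80% power is reproduced. The enrolment target of 60 leaves a margin of 60 − 52 = 8 patients, or 8/60 = 13.3%. This is the only drop-out figure in the protocol, and there is no AE rate.

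**Step 2: which drop-out causes count as AEs.**

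| Drop-out cause (11.1, 11.3) | Under 9.1.2 and 9.2 |
|---|---|
| Unstable circulation or respiration | AE, serious if potentially life-threatening |
| Arrest, reanimation | SAE |
| Emergency situation | AE if it involves such an impairment |
| Technical failure alone | Adverse device effect (ADE), not an AE |

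A pure device failure would not enter the AE numerator under any set.

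**Step 3: the gap.** Let n patients start, d drop out, e of the drop-outs have an AE, and c of the n − d completers have one.

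Gap = (e + c)/n − c/(n − d) = (d/n) × [e/d − c/(n − d)]

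The completers-only percentage is therefore too low exactly when the AE rate in drop-outs exceeds that in completers.

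**Step 4: illustrations.** Only 60, 52 and 8 come from the protocol. All AE counts and the other drop-out numbers are assumptions.

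| Assumption | All started | Completers only | Gap (points) |
|---|---|---|---|
| 8 drop-outs, all with an AE; 3 completers with one | 11/60 = 18.3% | 3/52 = 5.8% | 12.6 |
| Same, but the 8 are replaced so that 60 complete | 11/68 = 16.2% | 3/60 = 5.0% | 11.2 |
| 8 drop-outs, all with an AE; 20 completers with one | 28/60 = 46.7% | 20/52 = 38.5% | 8.2 |
| 2 drop-outs, both with an AE; 3 completers with one | 5/60 = 8.3% | 3/58 = 5.2% | 3.2 |
| 8 drop-outs, 6 of them device failures without an AE; 20 completers with an AE | 22/60 = 36.7% | 20/52 = 38.5% | −1.8 |

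Check of the first row: (8/60) × (8/8 − 3/52) = 0.1333 × 0.9423 = 0.1256. Check of the last row: (8/60) × (2/8 − 20/52) = 0.1333 × (−0.1346) = −0.0179.

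**The case against.** The best counter-argument is that the text already scopes the exclusion. In 11.1 and 11.3 it follows directly from the statement about the primary parameter, and the per-protocol set is itself defined by effects on that parameter. The authors may well have meant HF only. This stands as a reading of intent. It does not settle the wording, because 11.1 speaks of the study as a whole, 11.3 of the statistical analysis as a whole, and 11.6.3 offers nothing else.

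A safety set is often left to a separate statistical analysis plan, and none is at hand here. But section 11.4 refers only to 11.6, and a plan that added a safety set would depart from 11.1.

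Three further objections hold and limit the point:

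- Section 11.5 adds little. A patient who arrests lacks HRV data but has an AE on record, and the same section says that such losses will be reported.
- The AE counts in the illustrations are invented. Section 9.1.2 counts changes of more than 30% from baseline as AEs, so AEs in completers may be common, which narrows the gap.
- Practical visibility is good. Interruptions are summarised (11.1), AEs and SAEs go to the ethics committee and an SAE pauses the study (9.5, 9.5.1), SAE documentation is monitored (12.3.1), and a CRF is kept for non-completers (12.1.1).

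A reader might infer that an arrest or reanimation could never appear in the AE percentages. The protocol does not support that. The set requires treatment with both modes, not completion of both hours, so a patient who arrests in the second period has been exposed to both. Section 11.1 says only that drop-outs may occur after an interruption, and the protocol does not expressly equate compulsory withdrawal under 7.3.1 with drop-out under 11.1. Nor does the protocol conceal these events: what is at issue is the percentage, not the reporting of cases.

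**Conclusion.** The point holds as a defect in a stated rule, and it should be fixed. As written, the AE percentages omit patients excluded as drop-outs, and most listed causes of drop-out are, or may be, AEs or SAEs by the protocol's own definitions. The bias is downward if AEs are more frequent in drop-outs than in completers. The list of causes makes that likely but does not guarantee it.

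The size cannot be determined from the protocol. Under the assumed counts the gap runs from 12.6 points to −1.8. Confidence is medium, because the authors may have intended the exclusion for HF alone. The HF comparison and the sample size are not affected.

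**What to change.** 1. In 11.1 and 11.3, state that the per-protocol set and the exclusion of drop-outs apply to the efficacy endpoints (HRV and tidal volume) and the exploratory physiological endpoints.
2. In 11.6.3, state that AEs, SAEs and ADEs are reported with all patients who started at least one study ventilation period as the denominator, including those later withdrawn or replaced. Add that this applies as far as consent allows use of their data, because consent is sought only after extubation (7.1.1, 8.6.2).

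The cost is two or three sentences and one table. Section 12.1.1 already requires a CRF for every enrolled subject, including those who do not complete. If the authors meant the exclusion for HF only, the change merely says so.

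A split by ventilation mode at onset is optional. It needs the onset time or the mode to be recorded on the CRF: section 8.6.1 asks only for a date, and both modes run on the same day (Table 1).

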8.2.9 Procedures for subjects' compliance

All recordings will be performed by the investigators.

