8.2.10 Concomitant medication

All concomitant medications are allowed.

8.2.11 Interactions, reverse reactions and side effect of the medical device:

Not applicable. All devices used are part of the clinical routine ICU therapy. Both the conventional and variable PSV modes are part of the clinical routine ICU therapy. The arterial blood gas analyses are not part of the clinical routine ICU therapy. Potential risks and side effects of taking arterial blood gas analyses include infection and bleeding only in case of inappropriate usage.

8.3 Randomization and stratification:

Subjects will be randomized to the order of conventional and variable PSV treatment (first conventional PSV and then variable PSV or first variable PSV and then conventional PSV). The randomization will be performed by block-randomization using the online randomization program of the Medical University of Vienna (<https://www.meduniwien.ac.at/randomizer/web/login.php>). There will be no stratification of subjects studied. Only the statistician ([name]) and the responsible person performing measurements ([name]) will have access to the online randomization program.

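### The unblinded sole measurer also holds the randomization list, and the protocol describes no concealment of the next order from whoever includes the patient and sets the start time

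*Protocol*

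**What the plan says.** Section 11.1 of the protocol argues that reversed orders are unlikely because "measurements are done by one person", "who is also the holder of the randomization list". Section 8.3 sets out the method: "The randomization will be performed by block-randomization using the online randomization program of the Medical University of Vienna". It adds "There will be no stratification of subjects studied", and it names the statistician and "the responsible person performing measurements" as the only people who "will have access to the online randomization program". It gives no block size. Section 8.4 states that there is no blinding procedure; only the patient is regarded as blinded, because of his or her medical state.

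Table 1 lists inclusion first, randomisation second and the intervention third. Section 8.6.2 says that eligible patients will be included but not by whom. Section 8.2.9 says "All recordings will be performed by the investigators" and is silent on inclusion. Sections 7.2.2 and 8 describe one hour in each mode in randomized order, two hours in all without interruption.

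**The concern.** A list held by the person who runs the sessions may well reduce wrong-order errors. It also weakens the protection that randomizing the order is meant to give. In this design only the order is random, and the two periods follow each other directly. Random order is therefore what balances the natural drift of HF over the two hours between the sequences. All concomitant medication is allowed (section 8.2.10), so some drift within a session is plausible.

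If whoever picks the patient or the starting time can see or guess the next order, sessions expected to drift upward can be matched with conventional-then-variable, and sessions expected to drift downward with the reverse. Both choices push the variable-minus-conventional difference the same way and look like an effect of the mode. The arrangement is a stated part of the plan, presented as an advantage, so it is more than a detail left for a later document.

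**Working it through.** **1. The plan's own figure.** Inputs from section 11.2: difference 10 ms², SD of the within-patient difference 25 ms², two-sided alpha 0.05, 80% power. For a one-sample t-test the noncentrality is 10/(25/√n). At n = 51 the power is 79.99% and at n = 52 it is 80.8%, so the stated 52 is reproduced. Nothing in this point changes it.

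**2. What the sections establish together.**
- Sections 8.3, 8.4 and 11.1: one unblinded person measures, has access to the randomizer and holds the list.
- Table 1: inclusion comes before randomisation.
- No section: who includes the patient, who sets the start time, or whether an order can be seen before that patient is registered.

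If the list is a pre-generated sequence, its holder knows every coming order and the sequence in Table 1 conceals nothing from that person. If the online program issues orders one at a time, the holder knows only the past orders.

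**3. Predictability under one-at-a-time release.** The block size is not stated, so fixed sizes are assumed and known to the guesser. Enumerating all balanced blocks:

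| Block size (assumed) | Next order certain | Best guess correct |
|---|---|---|
| 2 | 50% | 75% |
| 4 | 33% | 71% |
| 6 | 25% | 68% |

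With a pre-generated list in hand, the next order is known for 100% of patients.

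**4. How selection enters the estimate.** Let τ be the true mode effect and T the mean natural change in HF from the first to the second hour, which may differ between sequences.
- Conventional first (A-B): E[V − C] = τ + T_AB
- Variable first (B-A): E[V − C] = τ − T_BA
- Mean over equal-sized sequences: τ + (T_AB − T_BA)/2

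Stable patient characteristics drop out of each line. A trend common to both sequences drops out of the mean. A gap between the trends remains, at half its size. The repeated-measures ANOVA of section 11.6.1 includes group, order and their interaction. In a two-period cross-over the interaction takes up the common period trend, but the group effect is still the mean of the two sequence-specific differences, so the half-gap stays in it.

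**5. Size under assumed gaps.** The protocol gives no trend figure, so the gaps are assumed as 0.1, 0.2 and 0.4 of the 25 ms² SD. The SE is 25/√52 = 3.47 ms². Type I error comes from the noncentral t with 51 df, critical value 2.008, and the SD held at 25 ms².

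| Trend gap (assumed) | Bias = gap/2 | Noncentrality = bias/3.47 | Two-sided type I error |
|---|---|---|---|
| 2.5 ms² | 1.25 ms² | 0.36 | 6.4% |
| 5 ms² | 2.5 ms² | 0.72 | 10.9% |
| 10 ms² | 5 ms² | 1.44 | 29.3% |

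The biases are 12.5%, 25% and 50% of the planned 10 ms² effect.

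**The case against.** The strongest reply is that the consequence is remote. Every patient receives both modes, so choosing sicker or healthier patients for one order does no harm to the within-patient contrast. Bias needs someone who knows or guesses the order, can foresee the two-hour HF trend, acts on it, and does so in opposite directions for the two orders. That stands. It makes the risk smaller than in a parallel-group trial, and the trend gaps above are assumptions with no source in the protocol.

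A second reply is that selective skipping would leave traces. Section 8.6.2 requires all patients scheduled for ICU to be screened, section 12.1 requires a log of eligible and non-eligible subjects with reasons for exclusion, and section 12.3.1 has the monitor verify the eligibility criteria. These help against skipping patients. They neither conceal the next order nor control the start time.

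Three stronger readings are tempting, and the protocol does not support them:
- A reader might infer that the measurer also includes the patients. No section says so; the wording on inclusion is passive, and section 8.2.9 concerns recordings only.
- A reader might infer that the next order is certainly known before inclusion. Table 1 puts inclusion first, and the word list could mean a pre-generated sequence or a record of orders already issued. The protocol does not settle which.
- A reader might count the deferred consent of section 8.6.2 ("Informed patient consent will be taken after the patients have been extubated and transferred to the normal ward") as part of the failure. Consent beforehand would not hide the order from someone holding the list, so its timing is not itself a concealment problem.

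**Conclusion.** The point holds in a limited form. The protocol places the randomization list with the unblinded person who makes every measurement, presents this as a strength, and describes no concealment of the next order from whoever includes the patient and sets the start time. A pre-generated list would defeat the sequence in Table 1. Release one at a time would still leave the order partly predictable, to a degree that depends on the unstated block size.

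The half-gap formula follows from the design. The type I error figures illustrate it: they rest on the assumed trend gaps, equal sequences, 52 analysed patients and an SD of 25 ms², and they do not estimate this trial's actual risk. The change should be made because it is cheap and because no planned analysis can remove the bias afterwards. The protocol gives no evidence that such selection will take place.

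**What to change.** In sections 8.3 and 11.1:
- Delete the arrangement by which the measurer holds the list, and the sentence that presents it as a protection.
- State who includes patients and sets the start time.
- Have the online randomizer release each order only after that patient has been irrevocably registered as included.
- Keep the list and the block sizes, preferably varying, with the statistician only.
- Guard against wrong-order errors by recording the released order on the CRF.

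This is a change of access rights in a randomizer already in use, plus one registration step per patient. Sample size, analysis and clinical procedures stay as they are. Because the measurer remains unblinded and sees past orders, varying hidden block sizes will reduce guessing but not abolish it.
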